## **Blood tests**

## Method

The full blood count test will be done using the Sysmex XT-1800 and Sysmex XT-2000 machine at the laboratory situated on the ground floor of the clinic. The platelet count will be measured using the hydrodynamic focusing (DC) detection mechanism, whereas the haematocrit level will be calculated via the red blood cell (RBC) pulse height detection method. Both of these methods will be performed by the Sysmex XT machine.

The dengue serology test will be performed using the Standard Diagnostics Dengue IgM capture ELISA, which is done at the medical virology laboratory in the main situated in the main hospital building. The mean sensitivity of this test is 97.6%, with a 95% confidence interval of 96.8%-98.4%. The mean specificity of this test is also high, which is 90.0%, with a 95% confidence interval of 88%-91.7%.

However, no confirmatory tests will be done such as PCR as such tests are very expensive, unavailable in the normal primary healthcare setting, and would not have an impact in the management of these patients. The IgG titres will not done for the participants in this study, even though many of whom have a paired sera sample. This was because this was not the standard practice for the laboratory handling the dengue serology specimens from the primary healthcare clinic.

## Tracing

Either the researcher or the trained research assistants will trace the full blood count daily using the online computer system for patient recruitment or follow-up purposes. The results of the dengue serology test will be traced one week after the date of testing. All the information obtained will be recorded on the data collection sheet.

## Defaulter tracing

For those who does not turn up for the follow-up with the researcher or the trained research assistants, an attempt will be made to contact the patient via the telephone, with a maximum of three attempts. During the telephone consultation, either the researcher or the trained assistant will attempt to find out the reason why the patient did not come for the follow-up appointment that was given. The patient will then be asked whether they will be amenable to come for follow-up the next day or at the next nearest date when convenient.

If the patient did not come for follow-up as he or she has been admitted to hospital, then details regarding the admission will be obtained. Such details will include which hospital they have been they admitted to, the date of admission, the reason for the admission and who recommended for the admission i.e. was it by medical personnel or did the patient themselves request for the admission. All these details would be entered on the standardized data collection form.

## Preliminary outcome measures

The outcomes will be assessed at the end of the two month period of data collection.

Several preliminary outcomes measures will be used to assess the trend of the preliminary results in order to determine the treatment effect size of the fluid chart. The two pilot study groups will be compared in terms of:

- 1. The hospitalization rates
- 2. The need for intravenous fluid treatment
- 3. The severity of haemoconcentration. Four surrogate endpoints were utilized to determine this, and they were as follows:
  - a. The mean peak haematocrit
  - b. The difference in haematocrit level between the values of clinic consultation 2 clinic consultation 1.
  - c. Those above the local cut off value of haematocrit indicative of plasma leakage.
  - d. Haematocrit fluctuation of 20% or more
- 4. With regards to assessing the severity of the platelet drop, two secondary endpoints were used:
  - a. The mean nadir platelet count
  - b. The difference in the platelet level between the values of clinic consultation 2 clinic consultation1.
- 5. The difference in the amount of oral fluid intake between the two groups.

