# Time frame of data collection:

The data will be collected from 1st June 2010 – 30th July 2010.

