# Follow-up

## Duration

All the patients recruited into the study will be followed up until they are clinically better and/or their laboratory markers show improvement as assessed by the respective doctors. Thus, different patients will be followed-up for different lengths of time.

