## **Estimated sample size**

This pilot study will be time driven, as the pre-specified time limit for data collection is two months. The minimum recruited number of participants required for each study group will be 30 patients, giving a minimum number of 60 patients in total. However, the research team strived to recruit as many patients as possible during those two months. This is to determine the actual treatment effect size, and the participant recruitment and retention rates to be used in the sample size calculation for the main evaluation trial.

A prior study has been conducted at the same primary healthcare centre that this pilot study will be performed, assessing outpatient management of dengue illness. This prior study hads a default rate of 16.4% amongst the outpatient suspected dengue cases, which was approximately half of the average default rate of patients attending the general outpatient clinic at University Hospital (33.8%) . However, the current default rate for suspected dengue patients at the primary healthcare clinic might have changed since then.

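### Recruitment, data collection and outcome assessment share one end date with no run-out, which conflicts with following the last recruits until they improve

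*Protocol*

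**What the plan says.** Three places in the protocol fix a single window.

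- Time frame of data collection: "The data will be collected from 1 st June 2010 – 30 th July 2010".
- Estimated sample size: "This pilot study will be time driven, as the pre-specified time limit for data collection is two months". The same section has recruitment fill that window: "the research team strived to recruit as many patients as possible during those two months".
- Preliminary outcome measures: "The outcomes will be assessed at the end of the two month period of data collection".

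Two other places set rules that run on each patient's own clock.

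- Follow-up, Duration: "All the patients recruited into the study will be followed up until they are clinically better and/or their laboratory markers show improvement", as judged by the treating doctors, and then "Thus, different patients will be followed-up for different lengths of time". No calendar end is given.
- Tracing: "The results of the dengue serology test will be traced one week after the date of testing".

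The protocol gives no last-recruitment date earlier than 30 July, no run-out period, and no rule for patients still under follow-up when the window closes.

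**The concern.** A patient recruited on 28 July cannot be followed to improvement, have serology looked up a week after testing, and also be fully assessed by 30 July. One of the rules must give way, and the protocol does not say which.

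If the fixed window prevails, the loss falls where events are expected. Entry requires at least three days of fever, and the protocol places the critical phase at illness days 4 to 6. A patient who enters on day 3 therefore has the whole critical phase still to come. Admissions among non-attenders are learned of only after a missed visit and up to three telephone calls, which adds delay. Intravenous fluid is assumed from admission, so a missed admission is also a missed fluid-treatment event. Peak haematocrit, nadir platelets and the differences between consultations 1 and 2 all need later visits.

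The Estimated sample size section says the pilot is to supply the effect size and the recruitment and retention rates for the main trial. Equal truncation in the two arms does not protect absolute rates. For fluid intake the truncation is not even equal. Controls give a 24-hour recall at recruitment, whereas intervention patients hand in charts only at a later visit.

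**Working it through.** **Plan's own figures.** From 1 June to 30 July inclusive is 30 + 30 = 60 days. The minimum sample is 30 + 30 = 60 patients. It has no power calculation behind it, so there is nothing further to reproduce.

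**Assumptions (not in the protocol).** Recruitment is even over the 60 days. Each patient needs L days of observation after recruitment. The short end, L = 4, is anchored in the protocol's phases: a day-3 entrant reaches the recovery phase (day 7) after 7 - 3 = 4 days. L = 7 and L = 10 cover slower recovery or later tracing.

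**Incomplete follow-up.** The share recruited within L days of closure is L/60.
- L = 4: 4/60 = 6.7%, about 4 of 60 patients
- L = 7: 7/60 = 11.7%, about 7 of 60
- L = 10: 10/60 = 16.7%, about 10 of 60

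**Missed admissions.** If admissions are spread evenly over the L days, a truncated patient loses on average half of that time. The share missed is (L/60) × 1/2 = L/120.
- L = 4: 3.3%
- L = 7: 5.8%
- L = 10: 8.3%

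The upper limit, with every admission at the end of the L days, is L/60, i.e. 6.7% to 16.7%.

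**Effect on a rate.** The Study setting section reports admission of 40% in April and 55.4% in March. These may include first-visit admissions, which the trial excludes, so they serve only as illustration.
- 40% × (1 - 4/120) = 38.7%; 40% × (1 - 10/120) = 36.7%
- 55.4% × (1 - 4/120) = 53.6%; 55.4% × (1 - 10/120) = 50.8%

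**Effect on a later sample size.** Take an assumed 50% versus 30%, two-sided 0.05, 80% power, 1:1. The usual two-proportion formula gives 93 per arm. If both rates are multiplied by (1 - L/120), the difference shrinks by the same factor. The result is 99 per arm for L = 4 and 108 for L = 10. At the upper limit of loss it is 105 to 125.

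**Effect on retention.** The definitions count a patient as a drop-out if never seen again after recruitment. Suppose recruits of the last d days are not yet due back at closure and are counted this way. Take the prior study's 16.4% default rate as an illustrative starting value. The apparent rate is 1 - (1 - 0.164)(1 - d/60).
- d = 1: 17.8%
- d = 3: 20.6%

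**Serology.** A sample taken after 23 July is due for look-up after 30 July (23 + 7 = 30). The Background says IgM first appears on illness day 4 to 5. A day-3 entrant tested then has a result 1 + 7 = 8 to 2 + 7 = 9 days after recruitment. If all recruits were such patients and all were tested, 8/60 = 13% to 9/60 = 15% of results would be pending at closure.

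**The case against.** The strongest reply is that nothing in the protocol says follow-up stops on 30 July. A reader might infer that late recruits are definitely cut off, but the Duration section points the other way, and neither telephone tracing nor serology look-up has a cut-off. Assessment at the end of the period could simply mean the time of analysis. This stands. The text supports a conflict between rules and a conditional truncation, not an established bias.

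A reader might also infer that late serology biases the pilot's key rates. It does not. Confirmed dengue is not among the objectives, the outcomes or the preliminary outcome measures. Testing is at the doctor's discretion, so the 13-15% above cannot be read as a share of all recruits. A second sample is mentioned in the diagnosis definitions but is not scheduled. Looking up a result also needs no return visit. Late serology leaves some final diagnoses pending and does no more than that.

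The third objection is size. A 3.3-8.3% relative loss moves a 50% rate to 48.3%-45.8%, a shift of 1.7 to 4.2 points. With 60 patients the standard error is √(0.5 × 0.5/60) = 6.5 points, a 95% interval of about ±13. The shift is small beside that. This too stands, although the shift always lowers the rate and is avoidable, which sampling error is not.

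Finally, the drop-out definition does not mention calendar closure, so counting late recruits as drop-outs is possible rather than prescribed. But the definition makes no exception for patients not yet due back.

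**Conclusion.** The point holds as a conflict that needs reconciling, with a modest and conditional consequence. The single 60-day window cannot be kept for the last recruits together with follow-up until improvement and the one-week serology lag.

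If 30 July is a hard stop, the figures for incomplete follow-up and missed admissions apply, and the absolute rates carried into the main trial are pulled down. Fluid intake, the outcome closest to the intervention, is lost unevenly: the truncated control's single value is a recall of the day before recruitment, and the truncated intervention patient has none. If data collection in fact stays open until the last recruit has improved, the truncated share is zero and only the wording is at fault.

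The sizes rest on even recruitment, an assumed 4 to 10 days of needed observation, and an assumed spread of admissions over that time. This is a cheap improvement, not a threat to the pilot's validity.

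**What to change.** Amend Time frame of data collection, Preliminary outcome measures and Estimated sample size to give two dates: one for last recruitment, and one for the end of follow-up, admission tracing and serology tracing. Either of these would do:

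- recruit to 30 July and continue follow-up data collection and tracing for about two more weeks; or
- stop recruitment about two weeks before 30 July and keep that date as the end of tracing.

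In both cases, state that outcomes are assessed once the last recruit's follow-up is complete. Add a sentence that a patient whose first return visit is not yet due is not a drop-out.

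The first option costs about two more weeks of tracing by existing staff; the second costs some recruits. Neither needs a new procedure or changes patient care.

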## Method of recruitment

#### Screening

All the patients presenting to the clinic with a history of fever for 3 days duration or more will be identified by the triage counter nurses. The clerk at the registration desk who handles the allocation of the patients to the various doctors working in the clinic for that working day would provide the following details on a separate list: the patient's name, registration number, identification card number and details as to which doctor's room the patient has been allocated to.

It is standard practice for the clinic that such patients would have a full blood count test done (blood is drawn by the respective nurses) mostly before the patient's consultation with their doctors. Since results of clinical investigations of patients are available online, either the researcher or the assistants would then trace the full blood count results from the computer. This will be done using the details provided on the daily working list which was mentioned earlier.

For patients with platelet counts of equal to or less than 150 x 10^9g/L, the researcher or the assistants will then find and tag the patient's clinic card and clinical notes in the various consultation rooms with a red tag. They will also remind the doctor who would be attending to the patient to re-direct the patient to the researcher's booth after the patient's consultation has ended if they suspected that the patient might have dengue fever, and if they were going to give the patient another appointment for outpatient monitoring.

The tag placed with the patient's clinic card also serve as a reminder for the attending doctors to redirect the patient to the researcher's booth after each subsequent follow-up consultation. This will be continued until the attending doctor is satisfied that the patient has completely recovered from the febrile illness either by clinical assessment or laboratory markers.

Thus the initial assessment of these patients and the subsequent follow-up consultations will be done by the various doctors working at the primary health clinic first. The researcher and the trained research assistants see the patients after the clinic consultation with their respective doctors had finished.

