## Severity of haemoconcentration:

#### Haematocrit fluctuation of 20% or more

This was calculated using the following standard formula:

Haematocrit fluctuation = (highest haematocrit – population baseline haematocrit) / population baseline haematocrit X 100%

The average population baseline haematocrit value for a 20 year old adult Malaysian male was 0.45 and for the average 20 year old Malaysian female was 0.38. These average population values were obtained and utilised with kind permission from [name] by personal communication based on her unpublished DENCO study data.

The author will use the average population baseline haematocrit rather than the individual patient's own values because no convalescent sample is routinely done for all the patients enrolled in this pilot study. Moreover, it has been shown by a prior study done in Vietnam which had correctly identified 94% of shocked patients as having capillary leak by utilising the local population mean haematocrit as the baseline for calculating the 20% fluctuation in haematocrit level.

Also, the length of patient follow-up varies from patient to patient depending on the attending doctor's assessment of the patient. This secondary endpoint is chosen as a measure for haemoconcentration based on the previous World Health Organization's guidelines for dengue, which included 20% fluctuation in haematocrit as one of the four diagnostic criteria for dengue haemorrhagic fever (DHF). A local Malaysian study also found a fluctuation of 20% haematocrit level to be highly associated with Dengue Haemorrhagic Fever (using the previous World Health Organization classification system).

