## Above the local cut off value indicative of plasma leakage

This is measured by calculating the percentage of patients achieving and surpassing the local Malaysian population cut off value for haematocrit to suspect plasma leakage. According to a recent study done on the Malaysian population, the cut off value that had been validated for Malaysian males was 0.47, and for the Malaysian females was 0.40^44.

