## Dengue phase of illness

The dengue phase of illness is based on the day of illness on recruitment into the study, which is as follows:

- The febrile phase is defined as day 1 of illness till day 3 of illness.
- The critical phase is from day 4 of illness to day 6 of illness.
- The recovery phase is defined as from day 7 onwards of illness.

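### Four severity endpoints are not limited to blood counts after allocation, so entry values can set them and pull any true effect towards zero

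*Protocol*

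**What the plan says.** Preliminary outcome measures lists "The mean peak haematocrit" and "The mean nadir platelet count" without saying from which visit the extreme is taken. The definition of the 20% fluctuation uses "highest haematocrit – population baseline haematocrit", divided by the population baseline, again with no start point. The local cut-off endpoint is obtained by "calculating the percentage of patients achieving and surpassing the local Malaysian population cut off value for haematocrit", with no time window.

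The first count precedes allocation. Screening describes "a full blood count test done (blood is drawn by the respective nurses) mostly before the patient's consultation with their doctors", after which "either the researcher or the assistants would then trace the full blood count results from the computer" to find patients with low platelets. Consent and then allocation follow at the researcher's booth, once the consultation is over (Recruitment and consent; Implementation of the random sequence).

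The consultation-1 count belongs to the outcome data: items 3b and 4b of Preliminary outcome measures subtract it from the consultation-2 value.

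Entry requires at least three days of fever and a platelet count already at or below 150 x 10^9/L. Dengue phase of illness classifies patients by their day of illness at recruitment: "The critical phase is from day 4 of illness to day 6 of illness", and the recovery phase starts on day 7.

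**The concern.** A value measured before allocation cannot be changed by the fluid chart, and its distribution is the same in both arms in expectation. Wherever it is the patient's highest haematocrit or lowest platelet count, or already lies over a threshold, the endpoint is fixed before the intervention starts. Such patients contribute noise but no treatment contrast.

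The entry criteria make this plausible. With day 1 as the day of fever onset, patients enter at the end of the febrile phase at the earliest, and may enter in the critical or recovery phase, when the extreme may be at hand or past.

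What is at stake is Study objective 3, the estimate of the treatment effect size. Dilution would make a useful chart look less useful on these measures.

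**Working it through.** **The plan's own figure.** Estimated sample size gives 30 per group: 2 x 30 = 60. No SD, effect size, event rate or power accompanies it, so there is no formula to reproduce. This point leaves the 60 unchanged.

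**Mean peak haematocrit.** Assumptions, none from the protocol: each patient has a stable level (it cancels), the within-person SD is 0.02, values are independent given that level, and the chart lowers every follow-up value by 0.01. X is the entry value and F the highest of k follow-up values, which average d above entry.

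Share recovered = [E max(X, F) − E max(X, F − 0.01)] / 0.01

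Simulation with 2,000,000 patients per setting:

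| d | k = 1 | k = 2 | k = 3 |
|---|---|---|---|
| 0 (no disease course) | 43% | 59% | 68% |
| 0.02 | 70% | 84% | 90% |
| 0.04 | 89% | 96% | 98% |

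Hand check for k = 1: F − X has SD 0.02 x √2 = 0.0283, and the share is close to Φ((d − 0.005)/0.0283). For d = 0, 0.02 and 0.04 this is Φ(−0.177) = 0.43, Φ(0.530) = 0.70 and Φ(1.237) = 0.89, which agrees. An endpoint restricted to follow-up values recovers 100% by construction. Nadir platelets follow the same logic with the sign reversed; the protocol gives no basis for a figure.

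**Local cut-off.** Baselines are 0.45 (men) and 0.38 (women); cut-offs are 0.47 and 0.40. The gap is 0.02 in each sex: 0.47/0.45 − 1 = 4.4% and 0.40/0.38 − 1 = 5.3%. If entry values centre on the baseline (assumed), the share f over the cut-off at entry is P(Z > 0.02/SD): 15.9%, 25.2% and 30.9% for SD 0.02, 0.03 and 0.04.

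**20% fluctuation.** Thresholds are 1.2 x 0.45 = 0.54 and 1.2 x 0.38 = 0.456, that is 0.09 and 0.076 above baseline. At SD 0.04, P(Z > 0.09/0.04) = 1.2% and P(Z > 0.076/0.04) = 2.9%; at SD 0.03, 0.1% and 0.6%.

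**Effect on a threshold contrast.** If q is the rate of new crossings among patients below the threshold at entry, the rate as defined is p = f + (1 − f)q, so the risk difference shrinks by the factor 1 − f. With assumed q of 40% and 20% and f = 30%: p = 0.30 + 0.70 x 0.40 = 0.58 and 0.30 + 0.70 x 0.20 = 0.44. The difference is 0.14 instead of 0.20. At two-sided 5% and 80% power, that needs 199 per arm. Counting new crossings needs 82 evaluable per arm, or 82/0.70 = about 118 recruited.

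**The case against.** The strongest reply is that no sentence says consultation 1 counts towards the peak or nadir, and that an assessment window is often left to an analysis plan. The first part is true, but it does not remove the problem. The protocol itself fixes these definitions, with formula and cut-offs, and they take an unrestricted extreme from a series that includes consultation 1.

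Other points stand and limit the claim:

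- **The size depends on the disease course.** If haematocrit rises well above its entry level during follow-up, little is lost. The protocol does not say which course applies.
- **Some baseline use exists.** The consultation 2 minus 1 differences already use the entry value as reference, so each severity domain has one measure free of this flaw.
- **The shares over the cut-off at entry are not estimates.** They rest on an assumed mean and SD. Patients who need admission at the first visit are excluded, and the Background says haematocrit and platelets inform that decision, which may lower the shares. Haemoconcentration already present at entry would raise them.

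A reader might also infer that patients who drop out necessarily have only a pre-intervention value, and might apply the 16.4% default rate to them. The protocol does not support this. Defaulted follow-up and drop out keeps the two terms apart and defines a drop-out as not returning to the research team. Clinic doctors see patients separately, and Tracing has full blood counts looked up daily online, so later counts may exist. No drop-out allowance is therefore made above.

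**Conclusion.** The point holds as a flaw in the definitions: as written, pre-allocation counts can determine all four endpoints. The pull towards zero is a statement about expectation and needs a true effect; if the chart does nothing, there is no bias, and in a single small pilot chance may run the other way.

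The size differs by endpoint and cannot be taken from the protocol. For peak haematocrit, between 43% and 98% of the assumed shift survives, depending on disease course and number of visits. For the local cut-off, the risk difference would shrink by about 16% to 31% under the baseline-centred assumption. For the 20% endpoint the loss is at most about 3%. Nadir platelets are exposed to the same mechanism, unquantified.

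A reader might infer that the effect size is understated as a matter of fact, or that the main trial will be sized on a diluted effect. Neither follows. The protocol also lists hospitalisation, intravenous fluid and oral intake, its aim concerns oral intake, and it does not say which outcome will drive the main trial's sample size. The risk arises only if one of these four measures is used for that purpose.

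**What to change.** - In Preliminary outcome measures and the two haematocrit definitions, state that all four endpoints use counts taken after allocation: consultation 2 onward, including later counts traced online.
- For peak haematocrit and nadir platelets, use the consultation-1 value as a baseline covariate. This adds an adjusted comparison to the Student's t test in Statistical analysis.
- For the local cut-off and the 20% fluctuation, count new crossings among patients below the threshold at consultation 1, and report those already over it as a baseline characteristic by arm. The subset is defined before allocation, so the randomised comparison is preserved.
- Report patients with no later count as missing, by arm, rather than letting the entry value stand in.

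**Cost.** Rewording only; no new data. Denominators shrink, possibly noticeably for the cut-off endpoint: at 16% to 31% over it at entry, about 10 to 19 of a minimum 60 patients would leave the comparison. Missing data also become visible, perhaps among the sickest, since Defaulter tracing collects details of an admission but lists no blood counts.

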# **Study population: Participants**

Inclusion criteria

All patients with the following:

[figure not shown]
- 1) Patients who are suspected to have dengue fever from the history and examination findings by a primary healthcare clinician.
- 2) History of fever for three days or more.
- 3) Thrombocytopenia: Platelets equal to or less than  $150 \ge 10^9$ /l.
- The platelet level of 150 x 10^9/L is chosen as the highest cut off point for thrombocytopenia because it is the lowest level of the normal range for platelets according to the University of Malaya Medical Centre's clinical laboratories. During the early febrile illness, the platelets and total white blood cell count are found to be lower among patients with dengue compared with patients with other febrile illness.
- 4) Age equal to or more than 12 years old. This is arbitrarily set to ensure that the patient concerned can understand instructions and fill in the fluid chart reliably and independently.

[figure not shown]

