## Method of intervention received by the intervention group

The patients assigned to the intervention group will be given a plastic cup of uniform size, along with a twenty four hour fluid chart. These patients will be instructed to use the cup for drinking any form of fluid they wish to consume for the duration of their participation in the study. Verbal instructions will be given on how to fill in the various details required on the fluid chart regarding their oral fluid consumption.

This will be done over the next twenty four hours or until they come for their next follow-up consultation at the clinic. If the next clinic follow-up will be given at the interval of a few days after the preceding consultation, then the researcher or the trained research assistant will provide enough fluid chart forms for the patient to fill until the next consultation.

The patient will be instructed to write down the amount of fluids they drank according to the time that they consumed the fluids in the second column. The patients will be instructed to record the type of fluids they drink in the third column. The patient will only fill the last column if they received any intravenous fluid drip over the next twenty four hours. They are to record the amount of bottles of fluid they receive intravenously.

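### The two consultation 1 to consultation 2 change endpoints mix day of illness and visit interval into the effect size meant for the main trial; the comparison should account for both

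*Protocol*

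**What the plan says.** All references are to the Protocol; no SAP is at hand.

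- **Endpoints.** Preliminary outcome measures lists 4b, "The difference in the platelet level between the values of clinic consultation 2 clinic consultation1", under the severity of the platelet drop, and 3b, "The difference in haematocrit level between the values of clinic consultation 2 clinic consultation 1", under the severity of haemoconcentration. I read both as consultation 2 minus consultation 1. Neither carries an interval or a day-of-illness window.
- **Interval.** Method of intervention received by the intervention group covers charting with "This will be done over the next twenty four hours or until they come for their next follow-up consultation at the clinic", then adds a case: "If the next clinic follow-up will be given at the interval of a few days after the preceding consultation". Defaulter tracing asks those who miss a visit to "come for follow-up the next day or at the next nearest date when convenient". Duration leaves follow-up to the attending doctors: "Thus, different patients will be followed-up for different lengths of time".
- **Entry.** The inclusion criterion is "History of fever for three days or more", with no upper limit.
- **Phase.** Dengue phase of illness classifies recruits by day of illness at recruitment: febrile to day 3, critical days 4 to 6, and then "The recovery phase is defined as from day 7 onwards of illness". The endpoints make no use of it.
- **Analysis and use.** Statistical analysis gives Student's t test for continuous variables. Allocation is by simple 1:1 randomisation. Study objectives (item 3) and Estimated sample size say the results will supply the treatment effect size for the main trial.

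**The concern.** A raw change between two visits measures the severity of a drop only if the visits sit at comparable points of the illness. Here one patient may be measured wholly on the way down, another across the turning point and a third wholly on the way up. All three are averaged as severity. The changes then partly cancel, and the between-patient SD contains the spread of entry days and intervals as well as the spread of disease.

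The pilot exists to hand an effect size and SD to the main trial. If those figures depend on how many late entrants this clinic happened to recruit in two months, they do not carry over to another case mix.

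**Working it through.** **The plan's own figure.** The only sample size is 30 per group. No effect size, SD or power is attached, so there is nothing to reproduce. For scale, at two-sided 0.05 and 80% power, 30 per group detects (1.960 + 0.842) × √(2/30) = 0.72 SD.

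**Assumed course (none of these figures is in the Protocol).** Platelets fall 20 per day to day 6, then rise 20 per day (×10⁹/L). Residual SD is 20. Entry day is uniform over the stated range, and the interval is 1, 2 or 3 days with equal frequency. The intervention slows the fall by 25%, to 15 per day, and leaves the rise alone.

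**Step 1: change by entry day and interval.**

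| Entry day | Control: 1, 2, 3 days | Intervention: 1, 2, 3 days |
|---|---|---|
| 3 | −20, −40, −60 | −15, −30, −45 |
| 4 | −20, −40, −20 | −15, −30, −10 |
| 5 | −20, 0, +20 | −15, +5, +25 |
| 6, 7 or 8 | +20, +40, +60 | +20, +40, +60 |

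The same disease course gives anything from −60 to +60.

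**Step 2: difference between arms.** The cell differences sum to 30 + 25 + 15 = 70 for days 3, 4 and 5, and to 0 from day 6.
- Days 3–8 (18 cells): 70/18 = 3.89. The control mean is (−120 − 80 + 0 + 360)/18 = +8.9, so the drop endpoint averages a rise.
- Days 3–6 (12 cells): 70/12 = 5.83. The control mean is −80/12 = −6.7.

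**Step 3: SD (control arm) and standardised difference.** SD = √(variance of the cell means left unexplained + 20²).

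| Analysis | Days 3–8 | Days 3–6 |
|---|---|---|
| Unadjusted | √(1343 + 400) = 41.8; 3.89/41.8 = 0.09 | √(1156 + 400) = 39.4; 5.83/39.4 = 0.15 |
| Adjusted for day (categories) | √(237 + 400) = 25.2; 0.15 | √(222 + 400) = 24.9; 0.23 |
| Day and interval, no interaction | 23.9; 0.16 | 24.6; 0.24 |
| Day, interval and interaction | 20.0; 0.19 | 20.0; 0.29 |

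Required sample size goes with SD². Adjusting for day alone multiplies it by (25.2/41.8)² = 0.36 for days 3–8, or (24.9/39.4)² = 0.40 for days 3–6.

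**Step 4: is the open interval alone the cause?** No. With a fixed 1-day interval the unadjusted values are 5/20 = 0.25 for days 3–5 and 2.5/28.3 = 0.09 for days 3–8. With 1–3 days they are 7.78/29.7 = 0.26 and 0.09. In this model the loss comes from entry day.

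**Step 5: case mix and error rate.** A second set of assumptions was simulated: fall 15 and rise 20 per day, noise SD 15, intervals 1–3 days, 30 per arm, 10,000 runs.
- The control mean change moves from about −1 to +24 as the share recruited on day 7 or later goes from 0% to 60%, with the disease course unchanged.
- With no treatment effect the t test rejects in 4.7% to 5.3% of runs.
- If the fall is halved, power is about 18%, 13%, 9% and 7% at recovery shares of 0%, 20%, 40% and 60%.

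**Step 6: chance imbalance.** With a recovery share q, the SD of the between-arm difference in that share is √(2q(1−q)/30). This is 0.103 at q = 0.2 and 0.126 at q = 0.4. By normal approximation, a difference of 20 points or more arises in about 5% and 11% of trials.

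**The case against.** **The direction of the counts is not in the document.** A reader might take the phase definitions as saying that platelets fall in the critical phase and rise in recovery. They give day ranges only. The turn is inferred from an endpoint named for a drop, a phase named recovery, and follow-up that runs until laboratory markers improve. That is enough for a drop followed by improvement, but not for a stated course by phase. This objection stands as a limit.

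**Bias.** A reader might infer that the arms would differ spuriously. The documents do not support that. Allocation is random, and the follow-up appointment is given at the consultation that precedes it, so entry day and booked interval balance in expectation. The simulated error rate stays near 5%. Imbalance in a single trial of 30 per arm is possible, but the t test already allows for it.

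**The open interval as a fault in itself.** Step 4 does not bear this out. The interval matters mainly in combination with entry day.

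**Failure of the whole severity assessment.** That does not follow. Peak haematocrit, nadir platelets, the local cut-off and the 20% fluctuation do not use this difference.

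**Pilot status and an unseen SAP.** This is a feasibility pilot, no single outcome is designated for the main-trial calculation, and covariate adjustment often sits in an SAP. This lowers the weight of the point. It does not remove it, because the Protocol itself fixes the raw difference and the t test and says the results feed the main trial.

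**Case mix.** Uniform entry on days 3–8 makes one third of recruits day 7 or later, and the Protocol gives no distribution. The days 3–6 column shows the case with no such recruits. The unadjusted loss remains there, because intervals still cross the assumed turning point and day-6 entrants only rise.

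**Conclusion.** The point holds as a loss of precision and interpretability in two endpoints. As written, 3b and 4b depend on when a patient enters and when the next count is taken, and the effect size and SD they pass on are specific to this pilot's case mix.

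Under the assumed course the standardised difference is 0.09 unadjusted against 0.15 to 0.19 adjusted for entry on days 3–8, and 0.15 against 0.23 to 0.29 for days 3–6. These sizes rest on assumed slopes, residual SD, entry days, intervals and a 25% slowing of the fall. They illustrate the mechanism and do not predict the trial. They are worked for platelets; for haematocrit the construct is haemoconcentration and no figures were assumed.

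**What to change.** In Preliminary outcome measures and Statistical analysis, state that 3b and 4b will be compared between arms by a linear model containing:
- arm;
- day of illness at recruitment, as categories or as the protocol's phase;
- days between the two counts, with the day-by-interval interaction if numbers allow;
- the consultation 1 value.

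Report the change by phase. Show recovery-phase recruits (day 7 onwards) separately from the severity estimates used to plan the main trial.

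Dividing the change by the number of days is tempting but does not help. For days 3–6 in the same model it gives 3.125/21.5 = 0.145, against 0.148 for the raw change, because it cannot undo an interval that crosses the turning point.

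**Cost.** The fix needs wording and a modest analysis. Day of illness is already defined at recruitment and counts are recorded at each visit; no visit or clinical decision changes. The model uses a few degrees of freedom, and the interaction may be too much for 30 per arm; without it the gain is mostly that of adjusting for day. Recovery-phase recruits do not contribute to these two severity estimates. Missed visits can shift the actual interval after allocation, so a check using the booked interval is sensible. The other preliminary outcome measures are unaffected.
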